This is a 5-year study to evaluate the effect of a 10-week patient-partner telephone-based cognitive behavioral stress management (PP-T-CBSM) intervention on chronic fatigue syndrome (CFS) symptoms in 150 CFS patients and their partners. Because many patients with CFS are unable to attend intervention sessions in clinical settings due to unpredictable periods of debilitating fatigue and limited mobility, we created a form of CBSM intervention that is delivered at the participant's home through a telecommunications system (Telephone-based CBSM) T-CBSM. A unique aspect of T-CBSM is that it uses the phone to convene groups of individuals in their homes—thus it retains some of the supportive elements of a group-based intervention. We have observed that over a 5 month period this patient-focused T-CBSM intervention is associated with decreases in CDC-based CFS symptoms and decreases in the pro-inflammatory cytokines and increases in anti-inflammatory cytokines. Greater decreases in pro-inflammatory cytokines were associated with greater increases in the negative pitch of the AM-PM slope of salivary cortisol and greater decreases in CFS symptoms. This supported our neuroimmune model as an explanation for the effects of T-CBSM on CFS symptoms. We also conducted subgroup analyses comparing partnered and unpartnered CFS patients and found that the effects of the intervention were much larger in the partnered group. We have designed a study to follow up on these findings by testing a newly designed partner-patient dual focus videotelephone-delivered CBSM intervention (PP-T-CBSM) that allows the partner to learn stress management techniques with the patient in a group format and to then practice together a set of stress management techniques such as relaxation and cognitive, behavioral and interpersonal skills training. We will compare changes in CFS symptoms, neuroimmune indicators, and psychosocial (patient and partner) functioning in participants assigned to PP-T-CBSM vs an attention time-matched telephone-based health information (T-HI) control condition in a 2 X 3 randomized experimental design with group (PP-T-CBSM, n=75 vs. T-HI, n=75) as the between-group factor, and time (Pre-intervention, 5- and 9-month follow-up) as the within-group factor.

PRIMARY AIM

AIM 1: To determine if PP-T-CBSM intervention improves CFS defining symptoms relative to participants in the T- HI condition.

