Hypoth 1.1 CFS patients assigned to PP-T-CBSM will show greater reductions in average CDC-based Symptom Frequency and Duration compared at 5- and 9-month follow-up vs. those in T-HI.

Hypoth 1.2 CFS patients assigned to PP-T-CBSM will show decreases in CFS symptoms of diarrhea, fatigue, muscle pain, unrefreshing sleep, sinus problems and general weakness, at 5- and 9-month follow-up vs. those assigned to T-HI.

SECONDARY AIMS

AIM 2: To determine if T-CBSM intervention improves di-urnal cortisol regulation and immune regulation (pro-inflammatory:anti-inflammatory cytokine ratio ([IL-1B+ IL-6 + TNF-x]:[IL-13 + IL-10]) relative to participants in the T-HI condition and how these changes relate to CFS symptoms.

Hypoth 2.1. CFS patients assigned to PP-T-CBSM will show greater reductions in pro-inflammatory: anti-inflammatory cytokine level ratio at 5- and 9-month follow-up compared to those assigned to T-HI.

Hypoth 2.2. CFS patients assigned to PP-T-CBSM will show greater increases in the AM-PM negative slope of salivary cortisol at 5- and 9-month follow-up compared to those assigned to T-HI.

Hypoth 2.3. The magnitude of reductions in CFS symptom frequency and severity from baseline

to 9 month follow-up will be associated with greater reductions in the pro-inflammatory: anti-inflammatory cytokine ratio and greater increases in the AM-PM salivary cortisol negative slope.

AIM 3: To test whether reductions in total and specific CFS symptoms and neuroimmune process indicators in PP-T-CBSM are associated with greater improvements in patient/partner psychosocial functioning (decreased stress, depression and social disruption and increased social support).

Hypothesis 3.1 Patients/partners assigned to PP-T-CBSM will show greater reductions in stress, depression and social disruption, and greater increases in social support at 5- and 9-month follow-up compared to those assigned to T-HI.

Hypothesis 3.2 The magnitude of reductions in CFS symptoms and pro-inflammatory cytokines and increases in the AM-PM salivary cortisol slope from baseline to 9 month follow-up are associated with greater decreases in stress, depression and social disruption and greater increases in social support.

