Given the small sample size available for analyses of intervention effects the interim results will be expressed as paired t-tests within the T-CBSM and T-HI groups for the period from baseline to 5-month follow-up. For the primary outcome—CDC-based CFS symptoms—we found that patients assigned to T-CBSM showed significant declines in average symptom frequency compared to T-HI. Patients assigned to T-CBSM also showed greater reductions in diarrhea, muscle pain, unrefreshing sleep, sinus problems and general weakness (p 's = .02 - .08) compared to no changes in the T-HI group. Those in the T-HI condition also reported increases in joint pain and abdominal pain, which were not seen in the T-CBSM groups. Similarly the T-CBSM patients showed decreases in SIP-Total Illness Burden Recreation and Pastimes compared with no similar change in the T-HI condition. In secondary analyses we observed changes in cytokine levels that mirrored these symptom findings. Here we found that those assigned to T-CBSM showed decreases in pro-inflammatory cytokines, IL-1 β and TNF- α and increases in the anti-inflammatory cytokine, IL-13, with no changes in T-HI. Greater decreases in TNF- α were associated with greater decreases in average CDC symptom severity over the pre-post intervention period. Greater TNF- α reductions also related to greater reduction in diarrhea, fatigue, muscle pain, joint pain, headache, and general weakness. Greater increases in the pitch of the negative AM-PM slope of salivary cortisol output (SP) were associated with greater decreases in TNF- α suggesting that a normalization of HPA axis function may relate to decreases in pro-inflammatory cytokines, which related to reduced CFS symptoms occurring during T-CBSM intervention.

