Rationale and Methodology

- 4.4. *** In non-technical, lay language, describe the study design and all study procedures, in order of sequence and timing. Include length of subject participation, what tasks are involved in the study, what tests or procedures subjects will be asked to complete or undergo, specific measures to be used, etc. If applicable, include frequency of visits, duration of visits, and study procedure calendar.**

Study Design:

This is a randomized controlled trial testing the effects of patient-partner based dual focused videotelephone-delivered CBSM (PP-T-CBSM) vs. a patient-partner attention-time matched health information control (T-HI). This study has a 2 X 3 (group: PP-T-CBSM, T-HI) X time (pre-intervention, about 5mo post, about 9 mo post) design with the primary outcome variable being total CDC-based CFS symptoms (frequency and severity). In addition we will explore selected individual symptoms to evaluate whether the intervention's overall effects are largely accounted for by specific symptom changes. The secondary outcome variable is a composite measure of pro-inflammatory cytokines: anti-inflammatory cytokines measured as the ratio of [IL-1B + IL-6 + TNF-x]: [IL-10 + IL-13]. The other secondary outcome variable is the AM-PM slope of salivary cortisol output over a 48hr sampling window (SP). We hypothesize that patients assigned to PP-T-CBSM will show larger decreases in CFS symptoms vs. those assigned to T-HI. We are also hypothesizing the greatest decrease in the pro-inflammatory: anti-inflammatory cytokine ratio and greatest increase in AM-PM negative SP in patients assigned to PP-T-CBSM vs. T-HI. We will examine whether changes in cytokines and cortisol are associated with psychosocial functioning to explain the effects of PP-T-CBSM on CFS symptoms. All analyses will control for medications, physical activity, and possible confounders per preliminary analyses. A total of 150 CFS patients and their partners between the age of 21 and 75 will be recruited for this study, with an anticipated retention of 124 at final assessment time point T3.

Study Procedures:

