4.11. *** Describe follow-up, data storage methods, data security, authorized access to records and record retention, including site name and address.**

Participant will have a total of 3 assessment time points, at the beginning of the study, and at approximately 5- and 9-month follow-ups. The participants will also be asked to provide samples of their saliva and blood at each time point. The screening forms, assessments, and consent forms will be safely stored at the Center on Aging ([name]) under double lock and key. Electronic information of the data will also be safely secured using access privileges and passwords. Saliva and blood samples will be stored in [name] lab in the E.M Papper Clinical Immunology Lab, Rosenstiel 8th Floor. Only study related personnel will have access to the participant's files.

4.12. *** Support the study validity by describing the statistical design, including quantitative and qualitative methods used to analyze data.**

The study is a 2 (experimental, control group) X 3 (pre-intervention, post-intervention, follow-up) randomized controlled design that will test the effects of a PP-T-CBSM intervention on hypothesized psychological, physiological and clinical/physical health indicators in a sample of patients diagnosed with CFS. Psychological data is derived from valid and reliable interview and questionnaire methods based upon published psychometric studies. Physiological data is derived from bioassays of collected biological specimens (blood, saliva) using standardized methods for quantitating concentrations of hormones and cytokines. The primary outcome is CFS physical symptoms and secondary outcomes include indicators of psychological and physiological functioning hypothesized to mediate the effects of the intervention on physical symptoms. Study hypotheses are tested using multivariate repeated measures statistical procedures designed to test for differences in the changes in study outcomes over time as a function of random assignment to study groups. Statistical controls (covariates) are employed where appropriate. All analyses have been guided by underlying theory and the study sample size was determined by power analyses based upon prior published work and pilot studies.

Privacy/Confidentiality Agreements

4.13. **Describe any privacy agreements or certificates of confidentiality, if applicable.**

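### The cytokine secondary outcome is a ratio of summed concentrations with no log scale or baseline adjustment stated, which can cost appreciable power and leaves its weighting to unreported analyte levels

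*Combined protocol and SAP*

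**What the plan says.** The Study Design part of section 4.4 makes the first secondary outcome "a composite measure of pro-inflammatory cytokines: anti-inflammatory cytokines measured as the ratio of [IL-1B + IL-6 + TNF-x]: [IL-10 + IL-13". Aim 2 in the opening summary gives the same formula, "IL-1B+ IL-6 + TNF-x]:[IL-13 + IL-10". Hypothesis 2.1 predicts "greater reductions in pro-inflammatory: anti-inflammatory cytokine level ratio at 5- and 9-month follow-up compared to those assigned to T-HI", and Hypothesis 2.3 relates change in the same ratio to change in symptoms.

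Section 4.12 says the assays work by "using standardized methods for quantitating concentrations of hormones and cytokines", and describes the analysis in one sentence: "Study hypotheses are tested using multivariate repeated measures statistical procedures designed to test for differences in the changes in study outcomes over time". Section 4.4 adds "All analyses will control for medications, physical activity, and possible confounders per preliminary analyses". The baseline value of the outcome is not named among the covariates.

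The plan gives no units, level, spread or detection limit for any of the five cytokines. It mentions no transformation or standardisation, and no power figure for this outcome.

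**The concern.** Two separate features of the formula matter.

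**Scale.** A quotient of two sums of positive, skewed quantities is itself right-skewed. A few patients with a small denominator can produce very large ratios and inflate the variance of a change score. A difference in raw ratios also depends on which sum is placed on top. On the log scale that choice only flips the sign.

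**Weighting.** An unweighted sum gives most influence to the analytes with the highest and most variable concentrations. In preliminary Study 3 (section 4.2, part C) the report of "decreases in pro-inflammatory cytokines" concerned IL-1 beta and TNF-alpha, together with a rise in IL-13. IL-6 and IL-10 were not named as changing. If those two sit at much higher levels, they can swamp the cytokines that responded.

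Hypothesis 2.1 and the cytokine part of Hypothesis 2.3 rest on this variable. The risk is a missed effect, and a choice of scale made after the data are seen. False positives are not the problem: simulated type I error was about 3.4 to 6.1% for every method tried.

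**Working it through.** **Inputs from the documents.** Allocation is "group (PP-T-CBSM, n=75 vs. T-HI, n=75) as the between-group factor". Section 4.4 expects 124 patients at the last assessment, so 124/2 = 62 per arm if losses are equal (124/150 = 82.7% retained). The plan has no power figure for this outcome to reproduce.

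**Inputs assumed, because the documents are silent.** Two-sided alpha 0.05; lognormal analytes; medians 1, 3, 8 (pro-inflammatory) and 5, 3 (anti-inflammatory); log-SD 0.5, 0.8 or 1.0; time correlation 0.5; analytes independent unless stated. The effect is −0.35 on the log scale for all three pro-inflammatory cytokines. Since exp(−0.35) = 0.705, this is a fall of about 30%.

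**1. Scale.** Let R = (IL-1B + IL-6 + TNF)/(IL-10 + IL-13). A uniform fall multiplies the whole numerator by 0.705, so log R shifts by −0.35 whatever the medians. This setting therefore isolates the effect of the scale. Simulated power:

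| Analysis | log-SD 0.5 | 0.8 | 1.0 |
|---|---|---|---|
| Change in R | 85% | 37% | 21% |
| R, baseline-adjusted | 97% | 58% | 32% |
| log R, baseline-adjusted | 99% | 77% | 55% |

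The relative loss from the raw scale alone compares the last two rows:
- log-SD 0.5: (99 − 97)/99 = 2%
- log-SD 0.8: (77 − 58)/77 = 25%
- log-SD 1.0: (55 − 32)/55 = 42%

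The step from row 1 to row 2 comes from baseline adjustment and has nothing to do with logging.

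If the analytes correlate at 0.3, baseline-adjusted power is 100/77/50% for R and 100/89/71% for log R. The losses are then 0%, (89 − 77)/89 = 13% and (71 − 50)/71 = 30%.

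With change scores on both sides and independent analytes, a separate run gave 84/36/20% for R and 96/64/44% for log R. The losses are about 12%, 44% and 55%.

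**2. Weighting.** With equal coefficients of variation and uncorrelated terms, analyte i carries mᵢ²/Σm² of the variance of its sum:
- equal medians: 1/3 each
- one analyte at 5 times the other two: 25/27 = 93%
- one analyte at 10 times the other two: 100/102 = 98%
- medians 1, 3, 8: 64/74 = 86% for the largest

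The answer is set almost entirely by levels that the plan does not give.

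**3. Which analytes respond.** Take a pattern like the pilot's (IL-1B and TNF down 30%, IL-13 up 30%), log-SD 0.8, time correlation 0.6 and between-analyte correlation 0.3. M is mean log(IL-1B, IL-6, TNF) minus mean log(IL-10, IL-13). The raw ratio and M are baseline-adjusted:
- IL-6 and IL-10 at 10 times the others: raw ratio 10%, log of the ratio about 15%, M about 99%.
- IL-6 and IL-10 at 3 times the others: 44%, 59% and 98%.
- TNF the large analyte: raw ratio 94%, M 99%.

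In the opposite case, where only a dominant TNF responds (log-SD 0.5), M has 55% against 96% for the baseline-adjusted raw ratio.

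Logging the finished ratio therefore deals with skewness but not with swamping. M deals with swamping but loses power when a single dominant analyte carries the effect.

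**The case against.** The strongest reply is that the plan never says the ratio will be analysed untransformed. Section 4.4 answers a form prompt that asks for lay language, and section 4.12 neither states nor excludes a log transform. That is fair: the raw scale is the plain reading of the text, not a stated commitment. It does not remove the point, because the choice between raw ratio, logged ratio and composite is still open and the three can disagree.

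A reader might infer that one high-concentration cytokine does dominate the ratio. The documents do not support that. They give no concentrations, and with equal medians each pro-inflammatory cytokine carries a third of the numerator variance. Dominance need not hide the effect either: TNF fell in the pilot, and if TNF is the large analyte little is lost.

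A reader might also infer that skewness halves the power. With baseline adjustment on both sides the loss stays below half up to log-SD 1.0. Setting raw change against a baseline-adjusted log ratio changes two things at once and overstates the effect of scale. Losses near or above half do appear with change scores at log-SD 1.0. They also appear with baseline adjustment at larger spreads: 39 to 50% at log-SD 1.2 and 53 to 62% at 1.5, in a separate set with time correlation 0.7. No figure in the plan places this trial at those spreads.

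Finally, the mean-log composite is a different estimand that weights every analyte equally, and the documents do not show that equal weights are better. This stands, and is why it should not replace the planned ratio.

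**Conclusion.** The concern holds in a limited form. As written, the plan points to testing change in a right-skewed ratio whose weighting depends on unreported levels. Over log-SD 0.5 to 1.0, the cost of the raw scale alone is about 2 to 42% of power with baseline adjustment on both sides and independent analytes, and less with positive correlation. Using change scores in place of baseline adjustment costs more again. The cost of weighting ranges from slight to nearly all the power, depending on which cytokines have the highest levels and which respond.

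All of these figures rest on assumed medians, spreads, correlations and effects. The more robust finding is the ordering: the baseline-adjusted log of the planned ratio had at least as much power as the raw ratio in every setting examined. This is a secondary outcome and the symptom outcome is untouched, so the change is advisable but does not threaten the trial's main conclusion.

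**What to change.** For Hypothesis 2.1, state that the outcome is the natural log of the planned ratio at 5 and 9 months, in a repeated-measures model with the baseline log ratio as covariate alongside the planned covariates. Report the arm difference back-transformed as a ratio of geometric means with a confidence interval. Use the same log scale for the cytokine part of Hypothesis 2.3.

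State common units for the five cytokines and one fixed rule for values below detection, both set before unblinding.

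Pre-specify mean log(IL-1B, IL-6, TNF) minus mean log(IL-10, IL-13), baseline-adjusted, as a supportive analysis. It protects against swamping by analytes that do not respond. Say in advance that it can be weaker when only the dominant analyte responds. Keep the raw ratio as a sensitivity analysis.

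The cost is wording only: same assays, same patients, same visits. There are two downsides. Results are on a geometric-mean scale, which differs from the ratio described elsewhere in the text. Logging also gives values near detection more influence, most of all in the supportive composite, so the below-detection rule matters.

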The CFS sample will be selected from the patient population of [name] CFS clinics (NOVA Univeristy and her Chronic Fatigue Center for Research and Treatment for Neuroimmune Disorders); community based physicians in Miami-Dade, Broward and Palm Beach Counties; and via community support groups, newspaper and web advertisements, and CFS related internet sites. Potential participants that contact us for information will be provided with a description of the study. If potential participant indicates having an interest in participating in the study they will be asked to complete a brief screening to determine eligibility (only the chronic fatigue patient will complete the screening interview). The screening process will take approximately 10 minutes (please refer to Screening Form in section 4.4A). Chronic fatigue patients will be screened and excluded for DSM-IV panic attack disorder, substance dependency, psychoses, with selected modules of the Structured Clinical Interview for DSM-IV (SCID). Patients who are diagnosed with one of these conditions during the course of the study will be excluded from data analyses and clinical referral will be provided as indicated. A modified Folstein Mini-Mental Status Exam and the Telephone Interview for Cognitive Status

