
Intervention Protocol:

After participants complete the interviews, and chronic fatigue patients complete the collection of saliva and blood, they will open an envelope that will advise them of the group they were randomly assigned to (PP-T-CBSM or T-HI). Participants who live outside our catchment area will be contacted to inform them of their randomization group. Randomization will occur in waves of eight, four dyads will be randomized to PP-T-CBSM and 4 to P-HI). Subjects randomized to PP-T-CBSM will receive 10 weeks of group intervention as described herein. A total of 4 dyads (CFS patient and their identified partner) will meet once weekly by videophone for approximately a one hour session at a mutually convenient set time. The content of the PP-T-CBSM protocol will comprise two broad domains: Cognitive, behavioral and interpersonal skills training and relaxation/imagery. The Cognitive, Behavioral and Interpersonal skills component presents information concerning stressors and stress responses from a biopsychosocial perspective. The initial 5 weeks emphasize: (1) the importance of appraisals in the stress response and in symptom occurrence; (2) understanding automatic thoughts and cognitive distortions; (3) identifying and monitoring automatic thoughts; (4) disputing and restructuring cognitive distortions into more rational thoughts, and (5) learning adaptive problem-focused and emotion-focused coping skills. By monitoring automatic thoughts associated with negative emotions, participants increase their awareness of cognitive appraisals that precede changes in emotion. Stressors of primary importance in this study are those concerning the physical symptoms of CFS and the losses associated with the illness. Participants learn how automatic thoughts, including cognitive distortions may contribute to symptom magnification and ensuing feelings of loss of perceived control. The remaining 5 weeks focus on

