Participants will incur no appreciable physical risks through participation in this study, though they may undergo psychological discomfort at some time points. During the psychosocial intervention, participants will be given specific CFS-related information, as well as be asked to participate in assessment of sensitive topics that may lead some to experience transient and mild anxiety. In addition, some participants are likely to manifest symptom increases from time to time throughout the longitudinal component of the study, and some may experience affective distress. In these cases, every attempt will be made to provide relief and to ameliorate the source of the discomfort. Should participants experience extreme acute or persisting affective reactions at any point during the study period, they will be referred to a psychiatrist or clinical psychologist associated with the site for care. In the event that a participant reports symptoms or concerns of extreme distress (e.g., severe symptoms of depression and/or anxiety suggesting clinical concerns, suicidality, etc.), our interventionists will directly target such symptoms and assess the severity of such distress within the group context while maintaining the group process and eliciting support from other participants. Subsequent to the intervention session, the participant will be contacted individually by one of the interventionists for a more comprehensive assessment of distress. If it is determined at that point that the participant needs individual care, our interventionists and research staff will

be prepared to refer the patient to a source of clinical intervention other than our PP-T-CBSM intervention (a list of referrals will be available). Similarly, should participants experience extreme, acute or persisting affective reactions at any other point during the study period (e.g., assessment, individual contact), they will be referred to the appropriate channels within the UM Department of Psychiatry or Psychology, as well as to a list of community resources/catchment sites in the South Florida area prepared to deliver resources to deal with extreme distress. Similar procedures will be followed for participants in our T-HI condition. The information obtained in this project will help in the development of strategies for promoting quality of life among individuals living with CFS. All participants will receive fair compensation for the time they invest in completing the research protocol.

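### Patients diagnosed with panic disorder, substance dependency or psychosis after randomisation are dropped from the analyses, so the comparison is no longer between the arms as randomised

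*Combined protocol and SAP*

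**What the plan says.** Section 4.4 (Study Procedures) sets the screening rule: "Chronic fatigue patients will be screened and excluded for DSM-IV panic attack disorder, substance dependency, psychoses", using selected SCID modules. The next sentence is a separate rule about the analysis: "Patients who are diagnosed with one of these conditions during the course of the study will be excluded from data analyses", with clinical referral where indicated.

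Randomisation comes later. Under Intervention Protocol in the same section, once the baseline interview and samples are complete, "they will open an envelope that will advise them of the group they were randomly assigned to". Ten weeks of intervention follow, then assessments at about 5 and 9 months. The opening study summary gives the design as "group (PP-T-CBSM, n=75 vs. T-HI, n=75) as the between-group factor".

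Section 4.12 says the hypotheses are tested by comparing changes over time according to random assignment. It names no analysis population. Neither it nor any other section describes an intention-to-treat analysis, a sensitivity analysis that keeps the diagnosed patients, or a limit of the rule to conditions present before randomisation. Section 6.4.A separately ends participation for someone judged dangerous to self or others who needs urgent mental health care. It does not say what happens to that person's data.

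**The concern.** A diagnosis made after allocation is a post-randomisation event. Removing patients because of it is harmless only if removal is unrelated to arm, or if those removed have the same outcomes as those kept. The plan secures neither condition.

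- **Occurrence.** The intervention is designed to change distress, so the chance of a psychiatric diagnosis may itself depend on the arm.
- **Detection.** No SCID is scheduled after screening, so later diagnoses depend on unscheduled contact. That contact differs in form: PP-T-CBSM is group work on stress and negative emotion, while T-HI is one-to-one health education. No blinding of the diagnostic judgement is described.
- **Outcomes.** The neuroimmune model in section 4.2 holds that distress worsens fatigue, and stress and depression are Aim 3 outcomes. Those removed may therefore differ on the primary symptom outcome and on the psychosocial outcomes.

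Every between-arm hypothesis rests on the randomised comparison. An analysis that omits these patients cannot show how large the resulting error is, or in which direction it runs.

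**Working it through.** **1. Does the rule reach randomised patients?** A patient excluded at screening has no trial data to remove, and the preceding sentence already covers that case. The study continues through allocation, ten weeks of sessions and two follow-up assessments. Nothing limits the second sentence to the interval before allocation. On its plain wording, it reaches randomised patients.

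**2. The plan's own figures.** The plan has 150 patients, 75 per arm, "with an anticipated retention of 124 at final assessment time point T3". Retention is 124/150 = 82.7%, or 62 per arm if losses are equal. The sample size cannot be reproduced, because alpha, power, effect size and SD are not stated. The retention figure makes no separate allowance for diagnosis-based removal and gives no information on how often it would occur.

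**3. Bias formula.** Let a share f of an arm be removed, and let those patients average D SD worse than the rest of that arm. If the retained mean is R, the full-arm mean is (1 − f)R + f(R + D) = R + fD. The retained mean is therefore better than the full-arm mean by fD. With the same D in both arms:

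bias = (f1 − f2) × D, in favour of the arm with the larger f.

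**4. Assumed inputs (not in the documents).** Take a difference in removal of 4 to 8 percentage points, which is 0.04 × 75 = 3 to 0.08 × 75 = 6 more patients in one arm, and D = 0.5 to 1 SD.

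- Lower end: 0.04 × 0.5 = 0.02 SD
- Upper end: 0.08 × 1.0 = 0.08 SD

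**5. Type I error.** This assumes a two-sided 5% normal test of two means with no true effect. SE is taken from the stated arm size, without reduction for the removals.

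| Per arm | SE = sqrt(2/n) | Bias (SD) | Bias/SE | Type I error |
|---|---|---|---|---|
| 75 | 0.163 | 0.02 | 0.12 | 5.2% |
| 75 | 0.163 | 0.08 | 0.49 | 7.8% |
| 62 | 0.180 | 0.08 | 0.45 | 7.3% |

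**6. Other assumed scenarios.** These use 62 per arm less the removals.

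| Removed, one arm vs other | Bias for D = 0.5 to 1 | Type I error |
|---|---|---|
| 3% vs 3%, or 5% vs 5% | 0 | 5.0% |
| 5% vs 10% | 0.025 to 0.05 SD | 5.2% to 5.8% |
| 2% vs 8% | 0.03 to 0.06 SD | 5.3% to 6.2% |

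**7. Power.** For an assumed d = 0.5, power with 62 per arm is 79.5%. Removing 2 to 12 of the 124 lowers it to between 78.9% and 75.4%. The loss of precision is small. The main issue is validity.

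**The case against.** The strongest reply is that nothing shows the rule to favour the intervention, and this stands. Section 4.7 says of extreme distress that "our interventionists will directly target such symptoms and assess the severity of such distress within the group context", which suggests closer observation in PP-T-CBSM. The same section then applies similar procedures in T-HI, and section 4.4 matches T-HI for contact time, delivered individually. One-to-one sessions might reveal a disorder as readily as a group of four dyads. If the intervention prevents such disorders, the bias could run against it.

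Three stronger readings are tempting, and the documents do not support them.

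- **That the rule removes the worst outcomes.** No outcomes are reported for such patients, and the primary outcome is CFS symptoms rather than psychiatric status. The link through distress is the protocol's hypothesis, so the most that can be said is that the rule may remove poor outcomes.
- **That anyone who deteriorates psychologically disappears.** Only three diagnoses trigger removal. Depression and general distress do not.
- **That harm is hidden.** The rule concerns data analyses. Section 16.2.A gives a DSMB review of adverse and serious adverse events, and nothing takes these patients out of that review.

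It is also fair to say that few new cases may arise in about nine months among patients already screened for the same disorders. That limits the likely size but does not justify the rule, since the number by arm is unknown in advance.

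**Conclusion.** The point holds. As written, the plan removes randomised patients from the analyses because of an event that may depend on the arm, and no analysis of all randomised patients offsets this. That contradicts the random-assignment comparison in section 4.12.

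The direction is unknown and the size cannot be determined from the documents. Under the assumed inputs the bias is modest: 0.02 to 0.08 SD towards the arm that loses more patients, with type I error of about 5.2% to 7.8% at 75 per arm. It is zero if removal and outcome difference are equal across arms. The conclusion that the rule should change rests on its wording and on the missing offset. It does not depend on these illustrative figures.

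**What to change.** Replace the analysis-exclusion sentence in section 4.4 and complete section 4.12 so that the plan states:

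1. Panic attack disorder, substance dependency and psychosis are exclusions only before randomisation.
2. All randomised patients are analysed in their assigned arm, using all outcome data collected. This includes scheduled assessments after such a diagnosis where the patient continues.
3. The number of these diagnoses is reported by arm.
4. The analysis without these patients is a sensitivity analysis only.
5. Data from participants terminated under section 6.4.A are handled in a stated way, consistent with item 2.

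The referral and termination rules themselves stay as they are. Only the treatment of the data is at issue.

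The cost is a few sentences and one table of counts. No extra patients or visits are needed, because the 5- and 9-month assessments are already scheduled.
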